Official Title: Effects of a Hands Free Crutch on Walking Stability During Gait

Identifiers: NCT04978363 Unique Protocol ID: 202101408

Document Date: 11/23/2021

Hands Free Crutch

PI: [name]
IRB ID #: 202101408

Describe EACH of your subject populations

- *Include description of any control group(s)*
- *Specify the Inclusion/Exclusion criteria for EACH group*

Healthy able bodied adults.

Subject Inclusion Criteria:

- Male or Female
- Ages: 18 - 45
- Height between 5'2" and 6'6"
- Foot size that corresponds to available walking boots
- Healthy individuals without current complaint of lower extremity pain, spine pain, open wounds or active infection
- Full active pain free range of motion of the bilateral upper and lower extremities and spine
- Able to hop without pain
- Able to perform a full squat without pain
- Able to walk up and down a flight of stairs at normal walking speed without using the hand rail
- Able to stand on one leg for at least 30 seconds
- Able to read and write in English and provide written informed consent

Subject Exclusion Criteria:

- Weight greater than 270 lbs
- BMI greater than 35
- Maximum thigh circumference at top of the leg greater than 28"
- Prior medical or neuromusculoskeletal disorders that have limited their participation in work or exercise in the last 6 months
- Prior lower extremity injury proximal to the ankle requiring surgery or limiting function for greater than 6 weeks
- Prior back pain that recurs or has limited activities for greater than 6 weeks
- Diagnosed moderate or severe brain injury
- Diagnosis of a physical or psychological condition that would preclude testing (e.g. cardiac condition, clotting disorder, pulmonary condition)
- Uncorrected visual or hearing impairment(s)
- Require use of an assistive device
- Pregnancy – Per participant self-report. Due to the expected small number of pregnant individuals, and resulting inability to account for its effect on resulting outcomes, participants will be withdrawn from the study

Provide a detailed description in sequential order of the study procedures following the consent process - DO NOT cut and paste from the Consent Document.

Describe study populations separately if they will be participating in different procedures - include CONTROL population if applicable.

- *What subjects will be asked to do/what happens in the study (in sequential order)*
- *The time period over which procedures will occur*
- *The time commitment for the subject for individual visits/procedures*
- *Long-term followup and how it occurs*

We anticipate the study will be completed in five sessions, with four biomechanical data collection sessions. The first session will require approximately one hour and each of the subsequent sessions will take approximately 2 hours each, for an approximate total of 9 hours. Although we will attempt to collect all data in the specific order listed, the number of study activities completed and the specific order of completion in each session will be dependent on participant, staff, and study equipment availability.

Potential participants will answer pre-screening questions as listed on the Pre-Screening Checklist over the phone before scheduling visit one, or in person during the first visit. If they meet all inclusion and exclusion criteria they will be consented to participate. Following consent, subjects will be screened using the post-screening checklist. If subjects fail to meet the inclusion or exclusion criteria, their participation will end at that point.

We will collect anthropometric and demographic information, have participants complete questionnaires concerning balance confidence and patient preference, and use a motion capture system to investigate effects of assistive device on walking stability, balance, and gait biomechanics.

Each participant will be given one overnight period to accommodate to the boot, SAC or HFC prior to collection. Participants will then undergo testing in each study condition (BOOT, HFC + BOOT/HFC NO BOOT, SAC + BOOT/SAC NO BOOT, and NONE) to determine how the boot and/or the assistive device affects stability through whole body or segmental angular momentum and gait biomechanics. We will use well-established techniques to obtain a range of biomechanical gait data as individuals walk at self-selected and a controlled speed.

Personal/demographic and anthropometric information (e.g. age, biological sex, height, weight, leg length, shoe type, shoe length and width) will be used to fully characterize the study participants. We will collect multiple variables that have been previously associated with outcomes, including race, ethnicity, and education to characterize the cohort.

Self-reported outcomes questionnaires will be used to evaluate participant balance confidence and device preference. These participant-centric assessments will provide insight that can be used to interpret other study findings. We have used the selected measures previously and expect that they will effectively capture device-related outcomes. Balance confidence will be assessed using the Activity-specific Balance Confidence (ABC) Scale, a reliable, valid, and sensitive self-reported assessment of balance. Device preference and device comfort will be assessed using standardized questionnaires, in a manner consistent with multiple other protocols. Participants will also report maximum pain with movement with use of the assistive devices on an 11 point numerical pain rating scale, in which 0 is no pain and 10 is the worst imaginable pain, consistent with other protocols and literature.

Techniques established and previously reported by [name] will be used to collect gait biomechanics data. Ground reaction force and motion capture data will be used to characterize the motion and loading of the lower limb and assistive devices as participants walk on a level walkway at self-selected speed and a controlled speed based on leg length. Ground reaction force and motion capture data will be used to evaluate the motion and loading of the lower limb as participants walk on an over ground walkway at self-selected speed and a controlled speed based on leg length. A minimum of three non-collinear reflective markers placed on the skin to minimize skin-bone movement will be used to determine kinematics for the segments of interest (foot, shank, thigh, pelvis, trunk, arms and head). A pointer wand with a rubber tip will be used to identify bony landmarks for segment coordinate system definition. Visual 3D software (C-Motion Inc.) will be used to calculate segment and joint angles and velocities. Force plates imbedded in the floor will capture ground reaction forces. Data from successful walking trials will be analyzed using Visual-3D software package (C-motion Inc., Germantown, MD).

Five total sessions, with four sessions including biomechanical data collection, are required for completion of this study. Participants will be contacted via phone or email that they provided during study enrollment. Three attempts will be made to contact each participant for each data collection session if they fail to attend data collection session(s).

Data and recordings will be stored on a password restricted drive that only authorized individuals have access to. They may be retained indefinitely for the purposes of evaluating data quality.

Describe the analysis methods you will use, including, if applicable, the variables you will analyze

AIM1

There are four conditions in this study Aim, 1) BOOT, 2) HFC + BOOT, 3) SAC + BOOT and 4) NONE. Between condition statistical comparisons for each hypothesis will be conducted in a similar manner for each dependent measure (e.g. whole body angular momentum and segmental angular momentum in all three planes: sagittal, frontal, and transverse). H1.1. Paired t-test will be used to compare the HFC + BOOT and SAC + BOOT conditions. H1.2. One-way repeated measure ANOVAs will be used to test for a condition effect across the 4 conditions: 1) BOOT, 2) HFC + BOOT, 3) SAC + BOOT and 4) NONE. Paired t-tests with Bonferroni-Holm correction will be used for post-hoc comparisons.

AIM2

H2.1 A one-way repeated measures ANOVA will be used to test for a condition effect across the 4 conditions (1) BOOT, 2) HFC + BOOT, 3) SAC + BOOT and 4) NONE) on self-reported balance confidence using the ABC scale. Paired t-tests with Bonferroni-Holm correction will be used for post-hoc comparisons. H2.2 Paired t-tests will be used to assess participant device preference between 2) HFC + BOOT and 3) SAC + BOOT for: the device numerical scale (0-10), the device comfort scale, and the numeric pain rating scale (0-10).

AIM 3

H3.1 Two-way repeated measures ANOVAs will be used to test for main, and interaction effects across the 6 conditions for the primary dependent measures:

- 1) BOOT, 2) HFC + BOOT, 3) SAC + BOOT
- 4) NONE, 5) HFC NO BOOT, 6) SAC NO BOOT

Paired t-tests with Bonferroni-Holm correction will be used for post-hoc comparisons.

Provide the rationale or power analysis to support the number of subjects proposed to complete this study.

The number of participants proposed for this study are consistent with those from prior investigations by [name] using angular momentum, which range from 10 to 30 participants. A total of 30 participants were included for this study due to the expected differences associated with the different mechanics of SAC and HFC use, along with the potential for post-consent screen failure, participant dropout in this study requiring repeat visits, or lost/missing data.

Literature cited / references (if attaching a grant or protocol enter N/A).

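### Condition order is neither randomised nor counterbalanced, and no analysis has a period term, so the HFC-versus-SAC comparison is open to order effects

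*Combined protocol and SAP*

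**What the plan says.** The study is fully within-person. The study-procedures section lists the conditions: "Participants will then undergo testing in each study condition (BOOT, HFC + BOOT/HFC NO BOOT, SAC + BOOT/SAC NO BOOT, and NONE". It also states that "Five total sessions, with four sessions including biomechanical data collection, are required for completion of this study". Before testing, "Each participant will be given one overnight period to accommodate to the boot, SAC or HFC prior to collection".

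On order, the same section says only that "we will attempt to collect all data in the specific order listed", and that "the specific order of completion in each session will be dependent on participant, staff, and study equipment availability". The wording covers data and study activities in general. Nothing else governs the order of conditions, and no text allots conditions to sessions. The idea of randomisation appears only in the title of a cited trial in the reference list.

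In the analysis section, H1.1 reads "Paired t-test will be used to compare the HFC + BOOT and SAC + BOOT conditions". H2.2 reads "Paired t-tests will be used to assess participant device preference between 2) HFC + BOOT and 3) SAC + BOOT". H1.2 and H2.1 use one-way repeated-measures ANOVA on condition. H3.1 uses a two-way ANOVA over six conditions laid out as boot by device. None has a period, session or sequence term.

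**The concern.** In a repeated-measures comparison, the time at which a condition is tested can affect the result. Participants may get used to the laboratory, the task and the rating scales, or they may tire. If HFC tends to come before SAC, or the reverse, that trend enters the paired difference and cannot be told apart from the devices. Random or balanced order normally prevents this. Here nothing makes the two orders balanced, and nothing in the analysis adjusts if they are not.

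H1.1 is the contrast most directly exposed. H2.2 is exposed to the extent that preference, comfort and pain are rated at each device's own session, and the questionnaire description does not say when they are rated. The plan also does not say that the order actually used will be recorded, and without that record the question could not be examined afterwards.

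**Working it through.** **Plan's own figure.** The sample size is 30, justified by earlier studies of 10 to 30 participants and an allowance for losses. No alpha, effect size, SD or power is given, so there is no calculation to reproduce. The point does not depend on the 30.

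**Inputs.** From the documents: n = 30 and a paired t-test of HFC + BOOT against SAC + BOOT. Assumed: two-sided 5%, a drift d between the two tests of 0.1, 0.2 or 0.3 SD of the paired difference, and k of 30 participants tested HFC-first. The documents give neither d nor k.

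**Two-period model.** With device effect δ, participant i's difference is N(δ + d, 1) if HFC-first and N(δ − d, 1) if SAC-first.

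- Bias = d × (k − (30 − k))/30 = d × (2k − 30)/30. At 24:6 this is d × 18/30 = 0.6d, that is 0.06, 0.12 and 0.18 SD. At 18:12 it is 0.2d. At 15:15 it is 0.
- Mixing orders also adds variance. The sum of squares follows a noncentral chi-square law with 29 df and noncentrality equal to the sum of squared deviations of the participant means. At 24:6 that is 24(0.4d)² + 6(1.6d)² = 19.2d². The rejection probability integrates the normal tail of the mean over this law.

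| HFC-first : SAC-first | False-positive rate (δ = 0) at d = 0.1 / 0.2 / 0.3 | Power at δ = 0.5 SD, opposing drift 0.3 |
|---|---|---|
| 15:15 | 4.9 / 4.6 / 4.1% | 72.4% |
| 18:12 | 5.0 / 5.1 / 5.2% | 61.1% |
| 21:9 | 5.4 / 6.6 / 8.5% | 49.1% |
| 24:6 | 6.1 / 9.3 / 14.6% | 37.4% |
| 30:0 | 8.3 / 18.5 / 35.5% | 18.5% |

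Power at 0.5 SD without drift is 75.4%. At 18:12 false positives hardly move, yet an opposing drift of 0.3 SD still lowers power to 61.1%.

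**Equal counts are not enough over four sessions.** Suppose a linear drift of d per session, with 15 participants tested HFC-first one session apart and 15 SAC-first three sessions apart. The bias is (15 × d − 15 × 3d)/30 = −d, and the false-positive rate is about 7.7, 14.7 and 24.1%. Session positions must be balanced as well as which device comes first.

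**What a period term can do.** In the two-period comparison it uses 28 df instead of 29 and multiplies the variance by 30 × (1/k + 1/(30 − k))/4.

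- At 15:15 the factor is 1, and power at 0.5 SD is 75.3%.
- At 24:6 the factor is 30 × (1/24 + 1/6)/4 = 1.56, and power is 56.2%.
- At any mixed split the false-positive rate returns to 5%.
- At 30:0 the term cannot be estimated.

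A rank check on a four-condition, four-session layout with 28 participants agrees. There are 28 + 3 + 3 = 34 parameters. One common order gives rank 31, and four Williams sequences of 7 participants each give rank 34.

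**The case against.** The strongest reply is that the harm is hypothetical. The order sentence is about activities and data in general, the overnight accommodation reduces early learning, and spreading the tests over several sessions limits fatigue. If drift is only 0.1 SD, the worst false-positive rate is 8.3%. If availability happens to give 18:12 or closer, it stays at or below 5.2% for every drift shown. All of this stands, and it limits the size of the point. It does not fill the gap: accommodation does not balance order, and if the order sentence does not govern conditions, nothing does.

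Three stronger readings are tempting, but the documents do not support them.

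- A reader might infer that everyone is tested HFC-first because HFC is named before SAC. The plan allows departures and does not say that the list of conditions is the test sequence. The 30:0 row is a worst case.
- A reader might infer that the condition lists contradict each other. They do not. The Aim 3 list is a 2 × 3 factor layout, and the accommodation sentence names alternatives joined by *or*. Neither is a test order.
- A reader might infer that the results are biased. No trend and no imbalance is shown.

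The illustration is also simpler than the design. It covers the HFC–SAC contrast with one drift size, and nothing was computed for H1.2, H2.1 or H3.1. Carryover from one device to the next is not modelled.

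**Conclusion.** The point holds as an omission with a cheap remedy. Condition order and the session map are not specified, no chance or balancing mechanism protects the HFC-versus-SAC contrast, and the planned tests cannot absorb an order effect. Confidence is high on the omission and the remedy, but not on the existence, direction or size of any bias.

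The exposure is negligible when orders are nearly even and session gaps are similar, apart from some loss of power if drift opposes the device effect. It becomes material when orders are clearly uneven and drift is 0.2 SD or more, for example 9.3 to 14.6% false positives at 24:6. These figures rest on the assumed drifts, splits and 5% level.

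**What to change.** For test conditions, replace the listed-order and availability rule with text such as:

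> Condition order will be assigned after post-consent screening and before the first biomechanical session, from a pre-generated randomised list, as balanced as possible for HFC-first versus SAC-first and for the session position of each condition (for example Williams sequences in blocks), with boot/no-boot order also balanced as far as numbers allow. Availability may move dates but not the sequence. The actual order and session of each condition will be recorded.

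State which conditions are tested in which session, and when the device ratings are taken. Add period (session) as a fixed effect, to protect against imbalance from dropout, departures or unequal session gaps.

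The text says *as balanced as possible* because an exact 15:15 cannot be promised. The 30 must also cover post-consent screen failures and "participant dropout in this study requiring repeat visits, or lost/missing data", and 30 does not divide evenly over four session positions.

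The cost is a short order list, some loss of scheduling flexibility (a visit may have to wait for the assigned device) and a few degrees of freedom. In the two-period comparison, the period term lowers power at 0.5 SD from 75.4% to 75.3% when there is no drift and orders are even. No extra participants, visits or equipment are needed.

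### Does Aim 1 leave the HFC + BOOT versus SAC + BOOT comparison with two competing verdicts?

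*Combined protocol and SAP*

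**What the plan says.** The relevant text is in the analysis methods section of the combined protocol and SAP, under AIM1.

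- The conditions: "There are four conditions in this study Aim, 1) BOOT, 2) HFC + BOOT, 3) SAC + BOOT and 4) NONE".
- H1.1: "Paired t-test will be used to compare the HFC + BOOT and SAC + BOOT conditions". No multiplicity correction is attached.
- H1.2: "One-way repeated measure ANOVAs will be used to test for a condition effect across the 4 conditions", followed by "Paired t-tests with Bonferroni-Holm correction will be used for post-hoc comparisons". The post-hoc pairs are not listed, and the text does not say whether a significant ANOVA is needed first.
- Both hypotheses use the same measures: "Between condition statistical comparisons for each hypothesis will be conducted in a similar manner for each dependent measure".

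The sample-size rationale says "A total of 30 participants were included for this study" and bases that number on earlier studies of 10 to 30 participants. It gives no effect size, standard deviation or power. No alpha level is stated in the document.

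**The concern.** HFC + BOOT and SAC + BOOT are both among the four H1.2 conditions. The ordinary reading of unlisted post-hoc tests after a four-condition ANOVA is all pairs, so the device pair would be tested once alone and once inside a Holm family. The participants, measure and t statistic would be the same, and only the threshold would differ. A measure could then be significant under H1.1 and not under H1.2.

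This is the central device comparison; the sample-size rationale appeals to expected differences between the two devices. Without a written order of precedence, one could fear that the more convenient verdict would be chosen after the data were seen. AIM2 avoids the problem because its four-condition ANOVA (H2.1) and its device t-tests (H2.2) use different scales. AIM1 has no such separation.

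**Working it through.** The plan has no figure of its own to reproduce here. N = 30 rests on precedent, not on a calculation.

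**Inputs.** From the plan: four conditions and 30 participants. Assumed: two-sided alpha 0.05, all pairs in the H1.2 family, Gaussian data with equal variances.

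**Number of pairs.** 4 × 3 / 2 = 6.

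**Thresholds.** H1.1 uses 0.05. Holm starts at 0.05/6 = 0.0083 for the smallest p-value and rises to 0.05/1 = 0.05 for the largest, provided every earlier step rejects.

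**Critical values at n = 30 (29 df).** The smallest significant observed difference in paired-SD units is t/√n.

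- At 0.05: t = 2.045, and 2.045/√30 = 0.373.
- At 0.0083: t = 2.832, and 2.832/√30 = 0.517.

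If the device pair is judged at Holm's first step, the verdicts split when the observed difference lies between 0.373 and 0.517 paired-SD. If the other five pairs have already been rejected, the pair faces 0.05 and the verdicts agree.

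**Direction.** A Holm-adjusted p-value is never smaller than the raw one. Any pair that Holm rejects is therefore also significant in H1.1. The reverse conflict was zero in every simulation run.

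**Frequency.** Simulated chance per measure of a significant H1.1 with a non-significant Holm result, n = 30, no ANOVA requirement, true device difference 0.3-0.5 paired-SD:

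| Position of the other conditions | Split verdict |
|---|---|
| All widely separated | 0% |
| Devices 0.5 SD above BOOT and 1.0 SD above NONE | 7-9% |
| HFC 1.0 SD from equal BOOT and NONE | 10-12% |
| HFC 0.5 SD from equal BOOT and NONE | 15-18% |
| BOOT and NONE equal to HFC, or midway between the devices | 21-28% |

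The range 0.3-0.5 is where splits peak. Across the same patterns, other true differences give:

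| True device difference (paired-SD) | Split verdict |
|---|---|
| 0 | 0-4% |
| 0.6 | 0-21% |
| 0.8 | at most about 5% |
| 1.0 | under 1% |

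At 0.3-0.5, requiring a significant ANOVA first moves the upper end from 28% to 29%. With dropout to 24 or 20 participants the range is 0-29%, or 0-31% with the ANOVA requirement.

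**What a change would buy.** Suppose the pair were tested only in H1.1 and Holm were applied to the other five pairs.

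- The first Holm step becomes 0.05/5 = 0.01. Power at that step for a 0.5 paired-SD contrast goes from 47.5% to 50.3%, a gain of 2.8 points.
- The chance of any Aim 1 false positive per measure goes from 7.8% to 8.4% when all four conditions are equal.
- It goes from 7.4% to 9.8%, a rise of 2.4 points, when the devices are equal to each other, BOOT equals NONE, and the two groups differ by 1.0 paired-SD.

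**The case for a change.** The strongest argument for a change is that it costs a few sentences. The plan neither excludes the device pair from the H1.2 family nor ranks H1.1 above H1.2, and at moderate effects a split verdict could occur on more than a quarter of measures in the least favourable patterns. The named examples (whole-body and segmental angular momentum, each in three planes) already give at least six measures on which this could happen. Writing down the natural reading would close the question before data are seen.

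The arithmetic in that argument stands, and so does the observation that the text is silent. The step from silence to defect does not. Both tests are pre-specified and tied to different questions: H1.1 asks about the two devices, and H1.2 asks whether condition matters across four settings. One planned contrast beside a corrected post-hoc family is a common layout. A report organised by hypothesis would show both results with the same raw p-value, leaving little room for hidden selection. The 21-28% range also needs BOOT and NONE to equal HFC or lie midway between the devices, together with a true difference of 0.3-0.5 paired-SD. The plan gives no effect size that points there.

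A further recurrence in AIM 3 ("main, and interaction effects across the 6 conditions for the primary dependent measures") cannot be relied on, because that section does not say which post-hoc contrasts follow the two-way ANOVA.

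**Conclusion.** No change to the plan follows. The possible double test is a gap in detail that an analyst fills sensibly: H1.1 answers the device question, and the Holm-corrected tests interpret the four-condition ANOVA. Followed as written, the plan gives a valid planned comparison beside a valid corrected family. No stated figure is wrong, and no estimate or confidence interval depends on the point.

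A split can run in one direction only. Its chance per measure is 0-4% with no true difference, 0-28% at 0.3-0.5 paired-SD, about 5% at most at 0.8 and under 1% at 1.0. These figures assume two-sided alpha 0.05, 30 participants and an all-pairs family, none of which beyond the sample size is stated in the plan.

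Taking the pair out of the Holm family would be a trade-off: 2.8 points of first-step power against up to 2.4 points more false positives in the scenarios examined. Letting the Holm-adjusted result govern would be equally defensible. Neither option deals with multiplicity across measures and planes, which is a separate and larger matter.

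### The H1.2, H2.1 and H3.1 repeated-measures ANOVAs drop anyone missing a condition although the plan expects missing data; fit mixed models with the same error strata to all observed data

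*Combined protocol and SAP*

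**What the plan says.** The analysis section names three omnibus tests:

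- H1.2, for each angular-momentum measure: "One-way repeated measure ANOVAs will be used to test for a condition effect across the 4 conditions".
- H2.1, for the ABC scale: "A one-way repeated measures ANOVA will be used to test for a condition effect across the 4 conditions".
- H3.1: "Two-way repeated measures ANOVAs will be used to test for main, and interaction effects across the 6 conditions for the primary dependent measures". The six conditions are listed as three device states, each with and without the boot.

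For follow-up, "Paired t-tests with Bonferroni-Holm correction will be used for post-hoc comparisons". H1.1 and H2.2 are paired t-tests.

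The sample-size rationale takes 30 participants, at the top of the 10 to 30 seen in prior studies, and mentions "the potential for post-consent screen failure, participant dropout in this study requiring repeat visits, or lost/missing data". It gives no rate. The study-procedures section describes five sessions, four of them biomechanical. It says that "the number of study activities completed and the specific order of completion in each session will be dependent on participant, staff" and equipment availability, and it provides for up to three contact attempts when a session is missed. No section defines an analysis set, an imputation method or a rule for participants with some conditions missing.

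**The concern.** A classical repeated-measures ANOVA works on a full participant-by-condition table. The plan does not announce a complete-case analysis; the restriction follows from the named method, and nothing in the text overrides it. Enrolling 30 people says how many start. It does not say how someone with three of four, or five of six, conditions is analysed. As written, that person's data stay out of the omnibus test.

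What is at stake is mainly the power of the omnibus tests. They can rest on clearly fewer people than the post-hoc comparisons that follow, since a paired t-test needs only two conditions. H3.1 is the most exposed because it needs six. H1.1, H2.2 and the post-hoc tests are much less affected.

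**Working it through.** **The plan's figure.** The 30 cannot be reproduced: the documents give no alpha, power, effect size, SD or loss rate. Nor do they map conditions to visits. Everything below therefore uses assumed rates.

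**Complete participants.** With an independent loss m per condition and k conditions, the expected number is 30 × (1 − m)^k.

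| m | k = 4 (H1.2, H2.1) | k = 6 (H3.1) |
|---|---|---|
| 2% | 27.7 | 26.6 |
| 5% | 24.4 | 22.1 |
| 10% | 19.7 | 15.9 |
| 15% | 15.7 | 11.3 |

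At 10%, a paired t-test keeps 30 × 0.9² = 24.3 people. With four conditions, 30 × 4 × 0.9 = 108 values are observed and 4 × 19.68 = 78.7 are used, so 29.3 are set aside. With six, 162 − 95.7 = 66.3 are set aside. If H3.1 is lost by whole visits, and there are four visits (BOOT; both HFC states; both SAC states; NONE), the k = 4 column applies.

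**Power.** Tests are at 5%, with effects set to about 80% power with 30 complete participants. That is a yardstick only; the plan claims no power.

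- Four conditions: correlation 0.5, one condition shifted by 0.5 paired-SD, 4,000 runs.
- Six conditions: same-device correlation 0.8 and otherwise 0.4, or all 0.5; 2,000 runs.
- Permanent dropout: leaving after one to three of the four visits.
- Ranges cover the correlation patterns and random or listed visit order.

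| Test and loss | Loss rates (%) | Planned ANOVA power (%) | Mixed model power (%) |
|---|---|---|---|
| 4 conditions, independent | 2 / 5 / 10 / 15 | 75 / 69 / 58 / 47 | 78 / 77 / 73 / 70 |
| 4 conditions, permanent dropout | 10 / 20 / 30 | 74 / 67–68 / 62 | 76 / 72–73 / 70 |
| H3.1 device, independent | 2 / 5 / 10 / 15 | 73–75 / 62–63 / 48–49 / 34–35 | 78–80 / 76–78 / 74–77 / 71–76 |
| H3.1 device, visits lost | 2 / 5 / 10 / 15 | 75–76 / 69 / 56–59 / 47–48 | 78–79 / 74–77 / 74 / 69–71 |
| H3.1 interaction, visits lost | 2 / 5 / 10 / 15 | 76 / 69 / 58–59 / 47–49 | 78–79 / 76–77 / 74–75 / 70 |
| H3.1 device, permanent dropout | 10 / 20 / 30 | 72–75 / 67–70 / 61–63 | 75–77 / 72–74 / 70–71 |

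A separate simulation of the four-condition case, using an F-test with participant fixed effects, gave 75/68/59/46% for complete cases against 78/76/73/69% for all data at 2/5/10/15% independent loss. At 10/20/30% dropout it gave 75/67/62% against 75/72/70%.

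**Agreement when nothing is missing.** In 400 simulated complete data sets for each design, the mixed models returned the uncorrected ANOVA's p-values to within 1e-9. Degrees of freedom were 87 for four conditions and 58/29/58 for device/boot/interaction.

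**Type I error, four conditions.** With 10–15% loss or 20% dropout under sphericity, it was 4.9–5.2% (model) and 4.9–5.1% (planned). With SDs two-fold apart, it was 5.9–7.0% and 5.8–7.2%.

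**Type I error, H3.1.** Across five covariance shapes with SDs up to two-fold apart, the model gave 4.6–7.0% (device), 4.6–6.9% (interaction) and 4.2–6.2% (boot). The planned test gave 4.9–6.8%, 4.7–6.2% and 4.3–5.6%.

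**Why the strata matter for H3.1.** With complete data and real participant-by-boot and participant-by-device variation, a participant intercept alone gave type I error 0.13 (boot), 0.09 (device) and 0.001 (interaction). The ANOVA's own strata gave 0.046, 0.048 and 0.053.

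**A side check on bias.** When dropout after the first session depended on the value observed there (about 17% dropout), the complete-case contrast was off by about 0.10 SD, with type I error 0.08. The mixed model was unbiased, at 0.058.

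**The case against.** The strongest reply is that the large gains need a loss pattern the documents do not support. Participants are healthy adults aged 18 to 45. The procedures text lists the two boot states of each device together, which suggests that losses would be correlated rather than independent. The sentence on session content can be read as being about which activity falls in which session, and the contact attempts as a retention measure. Screen failures leave nothing to recover. Under 10% permanent dropout the H3.1 device gain is only 1–3 points. The choice of 30 already contains some allowance: for a one-way design with 90% power at 30 complete participants, a simulation with approximate degrees of freedom put the planned ANOVA at 87% after 10% dropout (model 89%) and 80% after 20% (model 85%). All of that stands, and it is why the size must be read as a range.

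It does not remove the gap. The rationale itself anticipates dropout and missing data, and the allowance in N does not say how partial participants are analysed.

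Two technical objections also stand in part. For H3.1, the model's type I error can exceed the planned test's when SDs differ two-fold and whole visits are lost: 7.0% against 6.5% in one simulation, 7.9% against 6.1% in another. A Greenhouse-Geisser correction would address unequal variances within the planned ANOVA, but it does not bring back excluded participants. And keeping paired t-tests post hoc leaves them on a different set of people from the model. That is valid and the smaller change, although model-based contrasts would be an alternative.

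**Conclusion.** The concern holds and the change should be made; confidence is medium because the loss rate is unknown. The named ANOVAs exclude anyone lacking a condition, the plan expects such people, and no rule covers them. The gain for the H3.1 device effect runs from 1–3 points (10% permanent dropout) through 15–18 (10% of visits lost) to about 25–29 (10% independent loss). For four conditions at 10% it is about 2 points under permanent dropout (76 against 74) and 15 under independent loss (73 against 58). These figures rest on the assumed rates, correlations, effect sizes and visit map. If losses are rare, the gain is a few points at most.

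**What to change.** For H1.2, H2.1 and H3.1 only, replace the repeated-measures ANOVA by a linear mixed model on all observed data, using REML with Kenward-Roger degrees of freedom.

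- **H1.2 and H2.1:** fixed effect condition; participant random intercept (compound symmetry, negative variance estimate allowed). Report heterogeneous compound symmetry or unstructured covariance as a sensitivity analysis, because the main model shares the ANOVA's sphericity assumption.
- **H3.1:** fixed effects device, boot and their interaction; random intercepts for participant, participant-by-device and participant-by-boot, negative variance estimates allowed. Report unstructured covariance as a sensitivity analysis. With six conditions it has 6 × 7 / 2 = 21 parameters from at most 30 people and its convergence was not checked here, so state in advance what happens if it fails.
- **Unchanged:** paired t-tests for H1.1, H2.2 and the Holm-adjusted post-hoc comparisons.
- **Report** how many participants were measured in each condition, and how many in every one.

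The cost is SAP wording and somewhat more analysis work, with no new data. If everyone is complete, the planned uncorrected p-values are unchanged. The models rely on missing at random and share the ANOVA's sensitivity to unequal variances and correlations, with the mild H3.1 inflation noted above. They do not remove bias from device-related dropout, and they recover nothing from screen failures or from people who leave before any condition is measured.
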